## **Statistic Analyze**

The study used Two-way ANOVA repeated measures as a statistical analysis method, with effect size and improvement percentage (IP) as measures, and (IBM-SPSS statistics processor version 20) for data analysis. A statistical significance level of  $P \le 0.05$  (alpha) was used.

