# Feasibility of Home-Based Rehabilitation on Body Composition, some Anthropometric Measures and Muscular Strength after interruption 4-5 years of Spinal Cord Injury: Serial Cases Study on ISIS War Survivors in Iraq

## **Summary**

Background: The war in Mosul wrecked hospitals and rehab centers, leaving a gap in rehabilitation services. This resulted in a need for alternative solutions for rehabilitation. Objectives: This study aims to create a home-based rehabilitation program (HBRP) that fits the participant; surroundings, and also detect and evaluate how effective it is in improving body composition, some anthropometric measurements, and muscle strength after a (4-5) year break in rehabilitation.

Methods: This voluntary controlled trial included 18 volunteers split into three groups: 13 people with Spinal Cord Injury (SCI) their injuries time since (53.4-55) months. They joined voluntarily into Two groups, Eight in the experimental group (Exp.) and Five in the first control (1st Con.); while Five were healthy individuals in the second control (2nd Con.); all around (21.2) years old on average. The HBRP focused on muscles and whole-body joints by using the basic equipment and exercises right at the patient's homes. The program consisted of five weekly sessions with a gradually increasing achievement time of (45-120) minutes per session, participants were given rest time between exercises based on their level and severity of injury. The assessment was every three months.

Innovatively, this study stands out by introducing an HBRP tailored for individuals with SCI after interruption sustained (4 - 5) years ago. This unique approach not only addresses the challenges posed by the interruption of previous rehabilitation efforts but also seeks to uncover the efficacy of rehabilitation in these specific circumstances.

Conclusions: The study concluded that HBRP affected positively the muscles morphologically and functionally despite a stop in rehabilitation for a long period of (4-5) years for individuals with SCI.

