## The study raises two questions

Does the home-based rehabilitation program (HBRP) affect people with spinal cord injury through interruption of rehabilitation for 4-5 years?

Is the HBRP effects on variables such as body composition (Weight, BMI); Anthropometric Measures, and Muscle strength?

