#### Methods

This voluntary controlled trial included 18 volunteers split into three groups: 13 people with Spinal Cord Injury (SCI) their injuries time since (53.4-55) months. They joined voluntarily into Two groups, eight in the experimental group (Exp.) and Five in the first control (1st Con.); while five were healthy individuals in the second control (2nd Con.); all around (21.2) years old on average. As a first procedure, detailed interviews were conducted with each participant at the beginning of the study to gather information about their physical, psychological, and social well-being. This information helped the authors create personalized rehabilitation plans for each participant to ensure their

participation in the study for the entire 6 months period. Through our study objectives, the authors used body composition such as height, weight, BMI and some anthropometric measurements for body parts circumferences by using tape measurements, similar to a previous study by Akita et al. Also, muscle strength tests were performed on participants' lower and upper extremities, head, and trunk to measure various movements. The 2nd control group completed their measurements and tests at college. Additionally, a clinical test using the American Spinal Injury Association scale (ASIA) was conducted on each participant to assess sensory feeling and voluntary movement potential on both sides of the body.

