The physical tests were conducted using a handheld muscle tester called MicroFET2 to evaluate the strength of participants' lower extremities, head, and trunk by using unit measure kilogram (kg) 11. The Exp. group underwent a 6-month intensive rehabilitation program that involved whole-body exercises, including stretching, strength, endurance, and aerobic training, which was prepared based on previous studies 12. The program included five weekly sessions of (45-120) minutes, gradually increasing in intensity. It encompassed various exercises like bed exercises, rubber ball exercises for strength and balance, trunk flexibility exercises, crawling, rolling, ball-related movements, and exercises on parallel bars. Also, aerobic exercises targeted cardiorespiratory fitness. While weight exercises focused on the upper limbs, shoulders, chest, and back. Rest periods were personalized based on injury severity and overall health. The authors updated the exercises based on regular assessments every 3 months, tracking muscle strength and endurance. The authors created a contact link for coordination among medical, rehabilitative teams, and participants, families, overcoming some challenges within the Iraqi healthcare system.

To address complex complications like bed sores, renal infections, and muscle atrophy, the authors followed the method of psychological support. This method aimed to stimulate patients, willpower, encouraging them to overcome complications and emphasizing the benefits of rehabilitation for improved overall health and independence, by made WhatsApp group was created to facilitate information sharing and provide visual evidence of successful cases, inspiring and encouraging participants. Furthermore, the participant weight and BMI were monitored due to the potential impact of factors such as limited movement and hormonal changes on weight fluctuations, as recommended in previous studies.

The study highlights the participants the participants fidelity to treatment, as evidenced by positive outcomes and sustained progress beyond the conclusion of the therapeutic experiment. The participants demonstrated loyalty through ongoing communication with the main author, seeking feedback on their rehabilitation stages who reach it. Notably, some participants achieved the significant milestone of walking by standard walker with the assistive device Knee-Ankle-Foot-Orthosis (KAFO).

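### The analysis section does not say which ANOVA term or group contrast bears on the effect of HBRP, although one of the three groups is healthy, and it states one alpha with no outcome singled out

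*Protocol*

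**What the plan says.** The section headed Statistic Analyze is two sentences long. The first reads: "The study used Two-way ANOVA repeated measures as a statistical analysis method, with effect size and improvement percentage (IP) as measures", and adds the software. The second gives a significance level of 0.05. Neither names a term (group, time or group-by-time), a pair of groups, a primary outcome or a rule for multiple tests.

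Methods describes eight people with spinal cord injury (SCI) in the experimental group (Exp.) and five in the first control group (1st Con.). It adds, of the third group: "while five were healthy individuals in the second control (2nd Con". The setting of that group also differed: "The 2nd control group completed their measurements and tests at college". On timing, the Summary says "The assessment was every three months".

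The research question puts several outcome families side by side: "Is the HBRP effects on variables such as body composition (Weight, BMI); Anthropometric Measures, and Muscle strength". Methods refers to circumferences in the plural. On strength it first says "muscle strength tests were performed on participants' lower and upper extremities, head, and trunk" and then, for the handheld device, "to evaluate the strength of participants' lower extremities, head, and trunk". The second sentence omits the upper extremities. The Summary concludes that "HBRP affected positively the muscles morphologically and functionally".

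Section 5.9 of the Combined protocol and SAP lists a pre-post t-test, correlations and LSD. That form is titled as a community survey, and it ties none of these methods to the groups or outcomes of the home-based study.

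**The concern.** A repeated-measures ANOVA with three groups yields several p-values per outcome, and they answer different questions. With a healthy group included:

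- A group effect may only show that healthy people differ from people with SCI.
- A time effect is not specific to HBRP.
- The three-group interaction can arise when both SCI groups change and the healthy group does not.

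Of the available comparisons, group-by-time for Exp. versus 1st Con. is the one that sets these three explanations aside. The section does not name it, so a reader cannot tell which test supports the Summary's conclusion.

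A separate issue is that one alpha is given and no outcome is ranked. Any one of several unadjusted results could then be called significant.

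**Working it through.** The section derives no figure that could be reproduced; alpha is simply declared. The group sizes are consistent: 8 + 5 = 13 with SCI, and 13 + 5 = 18 in all.

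**Inputs from the Protocol:** n = 8, 5 and 5 (Methods); alpha 0.05 (Statistic Analyze); assessment every three months over six months (Summary, Methods).

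**Assumptions, not in the documents:** all three groups enter the ANOVA at baseline, 3 and 6 months; single-visit SD of 1; within-person correlation ρ of 0.5 to 0.9; no HBRP effect; healthy group 1 or 2 SD higher; or a linear gain of 0.5 SD shared by both SCI groups, with the healthy group flat.

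**Step 1. Which terms can be significant without an HBRP effect** (40,000 simulated trials per setting, % significant):

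| Term | ρ = 0.5 | 0.7 | 0.8 | 0.9 |
|---|---|---|---|---|
| Group, healthy +1 SD | 45.0 | 38.7 | 36.2 | 33.9 |
| Group, healthy +2 SD | 97.2 | 93.8 | 91.7 | 90.0 |
| Time, shared SCI gain 0.5 SD | 20.0 | 31.0 | 44.9 | 75.2 |
| Three-group interaction, same gain | 9.0 | 12.5 | 16.9 | 30.7 |
| Exp. vs 1st Con. group-by-time, same gain | 5.0 | 4.9 | 5.1 | 5.2 |

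**Step 2. Analytic check.**

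- *Group term.* The variance of the three-visit mean is V = ρ + (1−ρ)/3, and the noncentrality is δ² × (5×13/18)/V with F(2,15). For δ = 2 and ρ = 0.5, V = 0.667, noncentrality = 4 × 3.611/0.667 = 21.7, power 0.971. For ρ = 0.9, V = 0.933, noncentrality 15.5, power 0.898. If the SD of 1 is between-person only and the residual SD is 0.5, V = 1 + 0.25/3 = 1.083 and power is 0.847.
- *Interaction.* The SCI means deviate from their own average by −0.25, 0 and +0.25, so the sum of squares is 0.125. Noncentrality = 0.125 × 3.611/(1−ρ), which is 0.90 at ρ = 0.5 and 4.5 at ρ = 0.9. With F(4,30) the power is 0.092 and 0.310.
- *Time term.* The table weights the three groups equally. Weighting by group size gave 37.6% instead of 31.0% at ρ = 0.7.

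**Step 3. Number of outcomes.** Weight and BMI make 2. The plural for circumferences means at least 2. Strength regions number 3 or 4, depending on which sentence in Methods is used. The minimum is 2 + 2 + 3 = 7 or 2 + 2 + 4 = 8. Each region is counted once, although Methods mentions several movements.

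**Step 4. Chance of at least one false positive at 0.05 each.** If independent: 1 − 0.95^7 = 0.302 and 1 − 0.95^8 = 0.337. Simulated for 8 versus 5 people with equal correlation 0.3, 0.5 and 0.7, seven outcomes give 27.6%, 23.8% and 19.0%. Eight outcomes at correlation 0.3 give about 30–31%. The range is therefore about 19–31%.

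**Step 5. The Summary's joint conclusion.** This needs a positive result in favour of HBRP on both size and strength. With 2 circumferences and 4 strength tests, the false-positive rate is 0.5–2.4% for correlation 0 to 0.7. With 4 and 8 tests it is 1.7–4.4%.

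**Step 6. Precision of the proposed contrast.** The 95% CI half-width is t(0.975, 11 df) × √(1/8 + 1/5) = 2.201 × 0.570 = 1.25 SD of the change score.

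**The case against.** The strongest reply is that a controlled design with an SCI control group, analysed by two-way repeated-measures ANOVA, conventionally points to group-by-time, and that nothing shows another term was read as efficacy. The second half is correct. A reader might infer that a healthy-versus-SCI difference was actually reported as benefit; the documents do not support that. The first half helps less, because the default three-group interaction is still not the Exp. versus 1st Con. contrast.

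The simulations rest on inputs that the documents do not give. The section does not say that the healthy group enters the ANOVA, and the three-monthly assessment is not tied to any group. If healthy participants were measured once, or served only as a reference, Step 1 does not describe the analysis. No passage supports an equal gain in both SCI groups. The percentages therefore illustrate what can happen and do not measure this study.

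A reader might also infer a chance of about 30% that the Summary's conclusion is a false positive. That does not follow. The 30–34% is for any single positive result, and Step 5 shows that the joint rate is below 5% in every setting tried. The section also never says in so many words that 0.05 applies to all outcomes; this is inferred from one stated level and no singled-out outcome.

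Finally, for a study of 18 people whose title calls it a feasibility study and case series, compulsory adjustment is debatable. Holm's first step over seven tests has about 11% power for a 1 SD difference. That objection stands, and adjustment is optional below. It does not excuse leaving the contrast unnamed when the Summary states an efficacy conclusion.

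**Conclusion.** The concern holds in a limited form. The analysis section leaves open which term and contrast bear on HBRP, and with a healthy third group that choice can decide the conclusion. Provided that this group is in the ANOVA at all visits, the three omnibus terms can be significant in anything from about 9% to 97% of trials with no HBRP effect, depending on the term and the assumed inputs. The Exp. versus 1st Con. group-by-time test holds its 5%.

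Multiplicity is a separate and lesser issue. It matters for any single result called significant and has much less bearing on the Summary's joint statement.

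It would go too far to say that the contrast isolates the effect of HBRP. It does nothing about multiple outcomes, and people joined the two SCI groups by their own choice (Methods), so selection bias remains.

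**What to change.** **In Statistic Analyze:**

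1. State that evidence for HBRP rests on the group-by-time comparison of Exp. versus 1st Con., and that the healthy group is a reference only. State that group or time main effects and the three-group interaction are not evidence for HBRP.
2. If the contrast is chosen after the data were seen, say that it is post hoc.
3. Say whether the healthy group entered the ANOVA, and at which visits.
4. List every outcome tested, after reconciling the two lists of strength regions in Methods. Report each with an estimate and 95% CI, labelled exploratory. Holm adjustment is optional, for use if any result is called significant.
5. Say whether the methods in section 5.9 of the Combined protocol and SAP apply to this study. A pre-post t-test within one group shows only change over time.

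**In the Summary:** restate the conclusion as exploratory, limited to outcomes supported by that contrast, and note the voluntary group choice.

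**Cost:** a few lines of text, with no new data. The conclusion becomes softer and the intervals are wide, about ±1.25 SD of the change score. If Holm is used over 7–8 outcomes, the first step needs p ≤ 0.05/7 = 0.0071 or 0.05/8 = 0.0063, which is an observed difference of about 1.88–1.92 SD of change.

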## The main contributions of this study are:

To the best of the authors' knowledge, this is the first study in Iraq that highlighted the surviving victims of ISIS with SCIs.

The preparation of a home-based rehabilitation program (HBRP) that lasted for six months and that was compatible with the participants' living and environmental conditions as an alternative solution for conditions after the war also, at the time of the COVID-19 pandemic when everything was under the closure.

Assessing the effectiveness of rehabilitation on some anthropometric and physical variables in participants with SCI following participants' stopping of rehabilitation for (4-5) years after SCI.

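### Repeated-measures ANOVA with no missing-data rule drops anyone who misses a visit; one such SCI control would be 20% of that arm, and a matching mixed model would keep the visits that were observed

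*Protocol*

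**What the plan says.** The Statistic Analyze section of the Protocol is the whole analysis plan for this trial: "The study used Two-way ANOVA repeated measures as a statistical analysis method", in IBM SPSS version 20, at a 0.05 level. It has no rule for missed visits, dropout or incomplete cases.

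The Methods section gives the arms: "This voluntary controlled trial included 18 volunteers split into three groups". The two SCI arms are "eight in the experimental group (Exp.) and Five in the first control (1st Con.)", and a further "five were healthy individuals in the second control (2nd Con.)".

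On timing, the Summary says "The assessment was every three months", and the list of main contributions describes a "home-based rehabilitation program (HBRP) that lasted for six months". Together these imply baseline, month 3 and month 6. Neither document lists three visits as such. The Methods section ties three-monthly assessment explicitly only to updating the exercises, and the visit schedule of each control arm is not written out.

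The Combined protocol and SAP, section 5.9, was written for a wider survey. It names a pre-post t-test, correlations and LSD, also with no missing-data rule. Neither document states how many people were measured at each visit.

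**The concern.** The standard repeated-measures ANOVA procedure in SPSS takes one row per person and omits any row with a gap. (This is general knowledge of the software, not something in the documents.) With no rule stated, this deletion applies by default: one missed visit also discards that person's other visits.

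Complete data should not be taken for granted. The Methods section introduces its psychological support with the words "To address complex complications like bed sores, renal infections, and muscle atrophy", and the list of main contributions places the programme in the period of pandemic closures. If people in poorer health were the ones to miss a visit, dropping them could tilt the group-by-time comparison. Any deletion also costs precision, and arms of eight and five have little to spare.

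**Working it through.** Neither document gives a power, effect size, SD or dropout figure, so there is no planned figure to reproduce. The counts do add up: 8 + 5 = 13 with SCI, and 13 + 5 = 18.

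**1. Share of an arm lost with one incomplete person.** 1/5 = 20% of the SCI control arm; 1/8 = 12.5% of the experimental arm.

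**2. Precision of the experimental minus SCI control contrast.** With a common SD, the variance is proportional to 1/n₁ + 1/n₂.

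- 8 v 5: 1/8 + 1/5 = 0.325
- 8 v 4: 1/8 + 1/4 = 0.375; 0.375/0.325 = 1.154, so variance +15% and standard error +7.4% (√1.154 = 1.074)
- 8 v 3: 1/8 + 1/3 = 0.458; 0.458/0.325 = 1.41, so variance +41%

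**3. Power.** This is a simplified comparison of the two SCI arms alone: noncentral t, n₁ + n₂ − 2 degrees of freedom, two-sided 0.05 (sidedness is not stated). Effects are assumed, in SDs of the change.

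| Arms | Power at 1.5 SD | Power at 2 SD | Effect detectable with 80% power |
|---|---|---|---|
| 8 v 5 | 67% | 89% | 1.76 SD |
| 8 v 4 | 60% | 84% | 1.90 SD |

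The 95% confidence interval widens by 8.7% from 8 v 5 to 8 v 4.

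**4. How likely a deletion would be.** The missed-visit rate q is an assumption. If each of two follow-up visits is missed independently with probability q, the chance that at least one of n people is dropped is 1 − (1 − q)^(2n).

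| q per visit | At least one of 5 SCI controls | At least one of 13 with SCI |
|---|---|---|
| 2% | 1 − 0.98¹⁰ = 18% | 1 − 0.98²⁶ = 41% |
| 5% | 1 − 0.95¹⁰ = 40% | 1 − 0.95²⁶ = 74% |
| 10% | 1 − 0.90¹⁰ = 65% | 1 − 0.90²⁶ = 94% |

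**5. What a mixed model recovers.** Take one SCI control with one missed visit, all three visits as responses, known covariance, and an assumed within-person correlation ρ of 0.5 to 0.9. The target is the change from baseline to month 6.

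- *Only month 3 missed.* Both ends of the change are observed in all five controls. The variance stays at 0.325 and the whole loss is recovered.
- *Only month 6 missed.* The variance is proportional to 1/8 + R²/5 + (1 − R²)/4, where R² is the share of the variance of the change that is predicted by the baseline and month-3 values. The share of the loss recovered is therefore R².
  - Compound symmetry: 1 − R² = (1 + 2ρ)/[2(1 + ρ)]. At ρ = 0.5, R² = 0.33 and the variance is 0.125 + 0.0667 + 0.1667 = 0.358, so the standard error ratio is √(0.358/0.325) = 1.050. At ρ = 0.9, R² = 0.26 and the ratio is 1.055.
  - First-order autoregressive: R² = 0.5 at any ρ. The variance is 0.125 + 0.100 + 0.125 = 0.350 and the ratio is 1.038.

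These compare with 1.074 under deletion, so about a quarter to a half of the loss is recovered when month 6 is the missing visit.

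**The case against.** The strongest reply is that nothing shows that any visit was missed. The Protocol is written in the past tense and already states conclusions, so it reads as an account of finished work. The Methods section describes individual plans meant to keep people in for the six months, and reports continued contact. The Combined protocol and SAP, section 4.3, places testing mostly at home, which makes attendance easier. The complications are mentioned as something met with support, not as causes of absence. The rates in step 4 are pure assumption, and absences that cluster within a person would lower those chances. All of this stands. It means that the actual loss may be zero, but it does not supply a missing-data rule or a count per visit.

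Three stronger readings are tempting, and the documents do not support them.

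- A reader might infer that the results are already biased by deletion of sicker participants. No absence, and no link between illness and absence, is documented.
- A reader might infer that a mixed model keeps everyone and restores the power. It adds no follow-up data for a person who has none, and it recovers only part of the loss when month 6 is missing. If absence depends on values that were not observed, it too is biased. If the exclusion for non-commitment in section 5.3 of the combined form applies to this trial, the model does not bring those people back.
- A reader might infer that a baseline-covariate model with unstructured covariance, fitted to the 13 SCI participants, is a cost-free substitute. It leaves out the healthy arm, still drops anyone without a baseline value, and asks much of 13 people. Because the SCI groups were self-selected, adjusting for baseline can answer a different question from comparing changes, even with complete data. With month 6 missed by one control, its variance still rises by about 8–14%, against 15% under deletion.

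**Conclusion.** The point holds as a conditional weakness. The named method discards partial records, no rule says otherwise, and one incomplete SCI control would cost 20% of that arm and 15% in variance. At an assumed 2 SD effect, power would go from 89% to 84%. A method in the same software avoids all of that loss if only month 3 is missed, and about a quarter to a half of it if month 6 is missed.

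This rests on three inferred visits that apply to both SCI arms, on the default behaviour of the SPSS procedure, and on data missing at random. It does not show that any data were lost or that any result is wrong. The change is worth making because it is cheap and, in the form given under the fix, leaves the planned test unchanged if the data are complete. The larger limits remain: voluntary allocation, and a design that even with all 13 SCI participants has 80% power only for differences of about 1.76 SD.

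**What to change.** - State the assessment visits for each arm, and report the number measured per arm at each visit.
- Replace the ANOVA with a linear mixed model in SPSS MIXED (REML, Satterthwaite degrees of freedom). Use the baseline, month-3 and month-6 values all as responses, with group, visit and group-by-visit as fixed effects, all three groups kept, compound-symmetry covariance, and every observed visit used. With complete data this gives the planned ANOVA's group-by-visit test (the version that assumes sphericity, provided the estimated between-person variance is positive).
- Report the experimental minus SCI control difference in change from baseline to month 6, with its 95% confidence interval.
- State the missing-at-random assumption, and repeat the analysis under another covariance structure, such as first-order autoregressive.

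The cost is a few sentences and a different procedure in the software already named. If the analysis is already done, it is one re-run per outcome plus a table of counts. The downside is reliance on a simple covariance structure in a very small sample, which is why the sensitivity check is needed.
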